1.3 Non-Clinical and Clinical Study Findings

Potential Benefits

There is potential that patients who participate in this research trial will receive additional monitoring compared to patients who do not (as they are receiving follow up surveys), which could help with identifying infection sooner. Analyzing the efficacy of petrolatum with non-stick bandaging at resolving HS postoperative wounds and decreasing pain could help guide dermatologists' treatment of HS and

provide better outcomes for patients in the future, including those in this study that might pursue additional procedures in the future.

Risks

Risks of participation include distress in anticipation of post-operative wound management, pain and discomfort following the procedure and with dressing changes, and infection. However, these risks accompany normal clinical unroofing procedures. There is always a risk of confidentiality breaches, but we will be mindful and attempt to minimize this risk. Normal clinic protocol for post-operative pain management will be followed, which includes opioid and non-opioid analgesics depending on provider and patient preferences and needs. Pain with dressing changes can occur, especially with wet-to-dry dressings. Patients will be informed of this risk during their dressing change postoperatively and during their bandage training session with the nurse. Patients will be instructed to contact the clinic in the event that dressing changes are too painful so that additional pharmacotherapy can be prescribed and other wound management strategies discussed. Patients will be made aware of this risk so that they can opt out of the bandaging protocol if needed.

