5 STUDY INTERVENTION (DEVICE, DRUG, OR OTHER INTERVENTION)

- Description

Bandage: Petrolatum with Non-Stick Gauze

Petrolatum is a petroleum-based bioinert ointment that is non-irritating to the skin [8]. The petrolatum often feels soothing when applied and seems to minimize wound discomfort [2]. After placement of petrolatum, the wound is covered with nonadherent gauze and tape or another bordered dressing. This wound bandaging technique can be placed over the wound once or twice daily to maintain a moist wound base.

- Receipt/Storage

Petrolatum can be safely stored on the shelf at home.

- Treatment compliance and Adherence

Apply once to twice daily to the wound base. There are no other strict adherence requirements.

- Drug Return/Destruction

Petrolatum can be safely disposed of in normal trash receptacles.

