6 STUDY INTERVENTION ADMINISTRATION

- Randomization procedures

A stratified block randomization will take place after the principal investigator has left the surgical room following surgery. Randomization will be performed by the research fellow. Each participant is assigned to a particular stratum based on wound size and location, two important covariates to control for in statistical analysis given these variables can impact the Wound QOL survey and other results significantly. After strata assignment, randomization is completed via a RedCap algorithm. A detailed outline of the randomization process and groups can be found in **Figure 1**.

- Blinding procedures

Following the surgical procedure, the principal investigator will exit the exam room. The principal investigator will thus be blinded to the wound dressing technique as he will not be present for bandaging administration, but the patient will not be blinded as they themselves will be administering the bandaging at home.

- Unblinding procedures

If at any point unblinding occurs, the involved patient will be notified that their further participation in the study is voluntary but their patient data can no longer be used for analysis. There is no penalty or direct harm anticipated to the patient because of unblinding. They can continue to bandage their wound as assigned during randomization or alternatively if desired.

- Premature Study Closure

If any of the groups are showing significantly worse outcomes with regard to changes in pain or days to surgical wound resolution before the end of the recruitment period, the study will be ended prematurely.

- Subject Withdrawal

If a subject fails to complete a their one-week postoperative survey or are unable to complete the assigned wound care for a full week, they will be withdrawn from the study. All subjects will have the option to withdraw from the study at any time that they wish.

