8. DATA COLLECTION AND MANAGEMENT

All patient data collected in this study will be stored within the secure research software RedCap. Data access will be restricted to the research fellow as the primary data input source. Downloaded data will be secured on the UNC hospital cloud and only de-identified data will be sent via email. The principal investigator will not have access to any patient data until the de-identified data is provided for analysis at the conclusion of the study. Data will be coded according to established coding protocol.

Quality assurance is built into data collection process by ensuring that source data documents capture data in established/standardized format that aligns with establish coding standards.

Project manager will monitor data throughout the study to ensure all data is source verified. Data will be monitored after the first patient is enrolled, after the first 50% of patients are enrolled, and again at the end of the study (last patient, last follow-up). Regular meetings will be scheduled to ensure that data is cleaned along the way (not just at the end).

Data archiving: coded data will be stored on the Department share drive which is backed up and maintained by the school of medicine. Only study personnel will have access to the study data.

Data from patient surveys will all be collected at the same time so it is unlikely that we will be missing many data points. If patients fail to enter data at specific time points on their surveys we will use the previous value carried forward to the missing data point. The data for patients who do not return their surveys will not be included in the study analysis as it will be too difficult to correctly estimate their responses.

Data Safety Monitoring Plan

We will be compiling and monitoring data on responses on an ongoing basis and reviewing every 2-3 weeks. If one group is demonstrating significantly worse outcomes before the planned end of the enrollment period, we will end the study early and report the results available at that time.

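### Withdrawing randomised patients who miss the week-1 survey or a week of assigned wound care can bias all three primary comparisons, by an amount and in a direction the documents do not fix

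*Combined protocol and SAP*

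**What the plan says.** Patients are randomised on the day of surgery: "A stratified block randomization will take place after the principal investigator has left the surgical room following surgery" (section 6, Randomization procedures). The Subject Withdrawal item of the same section sets two conditions, "If a subject fails to complete a their one-week postoperative survey or are unable to complete the assigned wound care for a full week", and the consequence is that "they will be withdrawn from the study". It describes no further follow-up for these patients.

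Section 8 deals with missing data in two ways. For a missed time point, "we will use the previous value carried forward to the missing data point". For non-return, "The data for patients who do not return their surveys will not be included in the study analysis".

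Section 1.3 (Risks) states "Pain with dressing changes can occur, especially with wet-to-dry dressings", and adds "Patients will be made aware of this risk so that they can opt out of the bandaging protocol if needed". Section 4 says that all three primary endpoints (PUSH, Wound QOL, NRS) come from the online surveys that patients submit. PUSH is scored from the photographs sent with them.

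Section 5, on adherence to the petrolatum regimen, says "There are no other strict adherence requirements" beyond once or twice daily application.

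The documents define no all-randomised analysis set, no data collection after a patient stops the assigned dressing, and no missing-data sensitivity analysis.

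**The concern.** Both withdrawal triggers occur after randomisation, and the assigned dressing can bring either about. A patient who finds the changes too painful may stop the dressing or not return the survey, and pain with dressing changes is itself a primary endpoint. Patients know their arm. If loss is related to both arm and outcome, the patients analysed are no longer comparable groups formed by randomisation. Because every primary endpoint depends on the surveys, all three comparisons are exposed.

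Part of the loss is also avoidable. A patient who misses only the week-1 survey could still return weeks 2, 4 and 6, and week 2 is the visit at which the pain effect was sized. Carry-forward cannot help this patient, because there is no earlier survey value to carry. The 20% dropout allowance protects precision. It does nothing about selection.

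**Working it through.** **The plan's own figures.** Statistical Considerations gives 28 per arm, 2 more for covariates, 20% dropout and about 74 recruited.
- Reading the 2 as per arm: (28 + 2) × 2 = 60, and 60 / 0.80 = 75. Reading it as a total: 58 / 0.80 = 72.5, so 73. Both are close to 74.
- The 28 per arm matches the PUSH statement. At n = 28, (2.306 + 0.842) × √(2/28) = 0.841 SD, against 0.84 stated. The half-width is 2.306 × √(2/28) = 0.62 SD (0.60 with the normal quantile), against 0.61 stated.
- With 20% loss, 74 × 0.80 = 59.2, so about 59 patients would be analysed out of 74.

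**Inputs for the illustration.** From the documents: pain difference 1.3, SD 1.4, and 74 patients, or 37 per arm. The two-sided level of 0.025 is borrowed from the 97.5% interval stated for PUSH, because no level is stated for pain. Assumed, because the documents give no loss by arm: losses of 20%/5% and 30%/10% (wet-to-dry/petrolatum), and a correlation ρ of 0.3 or 0.6 between the tendency to be lost and worse pain.

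**Formulas.** In each arm the fraction q with the highest tendency to be lost is removed. Let c = Φ⁻¹(1 − q) and λ = φ(c)/(1 − q).
- The retained mean falls by ρλ SD.
- The retained variance is 1 − ρ²(cλ + λ²) times the original.
- λ is 0.350 at 20%, 0.109 at 5%, 0.497 at 30% and 0.195 at 10%.
- Observed pain difference = 1.3 − 1.4 × ρ × (λ wet-to-dry − λ petrolatum). For 30%/10% and ρ = 0.6: 1.3 − 1.4 × 0.6 × 0.302 = 1.05.
- Retained numbers: 37 × 0.80 ≈ 30 and 37 × 0.95 ≈ 35; 37 × 0.70 ≈ 26 and 37 × 0.90 ≈ 33.
- Power is from the noncentral t, with noncentrality (difference / pooled SD) / √(1/n₁ + 1/n₂).

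| Loss (wet-to-dry/petrolatum) | ρ | Observed difference | Pooled SD | n | Power |
|---|---|---|---|---|---|
| none | – | 1.30 | 1.40 | 37/37 | 95% |
| 20%/5% | 0.3 | 1.20 | 1.38 | 30/35 | 88% |
| 20%/5% | 0.6 | 1.10 | 1.32 | 30/35 | 85% |
| 30%/10% | 0.3 | 1.17 | 1.38 | 26/33 | 83% |
| 30%/10% | 0.6 | 1.05 | 1.30 | 26/33 | 78% |

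The fall in power combines the smaller numbers with the reduced difference.

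**When the bias is zero.** If q and ρ are the same in both arms the λ terms cancel. If ρ = 0 there is no shift at any loss rate.

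**PUSH.** If the same correlations applied to healing, the shift in the petrolatum minus wet-to-dry difference would be ρ(λ wet-to-dry − λ petrolatum). That runs from 0.3 × 0.241 = 0.07 SD to 0.6 × 0.302 = 0.18 SD. Higher PUSH is worse, so heavier loss of poor healers from wet-to-dry makes petrolatum look relatively worse and works against non-inferiority. Swapping the arms reverses the sign.

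**The case against.** The strongest reply is that nothing in the documents shows that loss will differ by arm or relate to outcome. This stands. The mechanism is well supported by section 1.3, but it is an inference, and the loss rates and correlations above are assumptions. A reader might infer that the rule certainly biases every primary comparison. The documents support only that it can.

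A reader might also infer that the rule tilts the trial towards non-inferiority. That does not follow. The loss pattern section 1.3 makes most plausible, heavier in wet-to-dry, would work against petrolatum on PUSH if those lost were the poor healers.

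A larger fall in power is tempting too. At 28 per arm with the SD held at 1.4 and ρ = 0.6, power drops from 87.5% to about 73% (20%/5%) or 69% (30%/10%). But the same selection narrows the SD, which gives 79% and 76% at 28 per arm. Starting from 37 per arm and taking off the assumed losses gives the 85% and 78% in the table.

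Two points of text also stand. Section 6 does not say that data collected before a withdrawal for non-adherence are discarded; outright exclusion is explicit only for unreturned surveys. And the sentence in section 5 describes the petrolatum regimen, while section 6 concerns being unable to do the care for a full week in either arm. A reader might call this a contradiction, but it is a matter of unclear wording.

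Finally, the synopsis gives official dates ending in October 2023, section 2.3 gives an actual enrolment of 74, and the document is dated 8/1/2024. Follow-up may be over, in which case new wording cannot recover surveys that were not sent.

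**Conclusion.** The point holds as a risk of attrition bias built into the plan. Two post-randomisation events, both of which the dressing can cause, lead to withdrawal, and non-returners are left out of the analysis. Nothing else in the documents offsets this.

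Under the assumed losses and correlations, the pain contrast shrinks by 0.10 to 0.25 points, or about 8% to 19% of 1.3 (0.10/1.3 and 0.25/1.3). Power is about 78% to 88% instead of about 95%. In most of these cases power stays above the planned 80%, so the main issue is the validity of the randomised comparison. The true size and sign are unknown, so readers of the results could not correct for the bias.

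**What to change.** Replace the withdrawal rule. Patients who miss the week-1 survey or stop the assigned dressing stay in follow-up unless they withdraw consent, receive the remaining surveys, and are analysed in their randomised arm using all available data. Record adherence. Report losses and their reasons by arm. Add a missing-data sensitivity analysis. Use a per-protocol set only to support the PUSH non-inferiority comparison.

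If follow-up is complete, apply this to the analysis set and the report: include every randomised patient with any returned survey, and disclose by arm who was withdrawn under the rule.

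As a minor item, clarify how the adherence wording in sections 5 and 6 fits together, and state whether data collected before a withdrawal are kept.

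The cost is small. No larger sample is needed, and up to 74 patients instead of about 59 could be analysed. For patients still in follow-up the work is a protocol amendment and continued emailed surveys; for those already finished it is analysis and reporting only.

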8. DATA COLLECTION AND MANAGEMENT

All patient data collected in this study will be stored within the secure research software RedCap. Data access will be restricted to the research fellow as the primary data input source. Downloaded data will be secured on the UNC hospital cloud and only de-identified data will be sent via email. The principal investigator will not have access to any patient data until the de-identified data is provided for analysis at the conclusion of the study. Data will be coded according to established coding protocol.

Quality assurance is built into data collection process by ensuring that source data documents capture data in established/standardized format that aligns with establish coding standards.

Project manager will monitor data throughout the study to ensure all data is source verified. Data will be monitored after the first patient is enrolled, after the first 50% of patients are enrolled, and again at the end of the study (last patient, last follow-up). Regular meetings will be scheduled to ensure that data is cleaned along the way (not just at the end).

Data archiving: coded data will be stored on the Department share drive which is backed up and maintained by the school of medicine. Only study personnel will have access to the study data.

Data from patient surveys will all be collected at the same time so it is unlikely that we will be missing many data points. If patients fail to enter data at specific time points on their surveys we will use the previous value carried forward to the missing data point. The data for patients who do not return their surveys will not be included in the study analysis as it will be too difficult to correctly estimate their responses.

Data Safety Monitoring Plan

We will be compiling and monitoring data on responses on an ongoing basis and reviewing every 2-3 weeks. If one group is demonstrating significantly worse outcomes before the planned end of the enrollment period, we will end the study early and report the results available at that time.

All patient data collected in this study will be stored within the secure research software RedCap. Data access will be restricted to the research fellow as the primary data input source. Downloaded data will be secured on the UNC hospital cloud and only de-identified data will be sent via email. The principal investigator will not have access to any patient data until the de-identified data is provided for analysis at the conclusion of the study. Data will be coded according to established coding protocol.

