1.4 Primary Objectives

Primary Outcome Measures:

- 1. Change in Wound QOL Survey Score Over Time
 - a. A validated Wound Quality of Life (QOL) Survey will be administered that focuses on patient-reported outcomes of level of wound pain, pain with dressing changes (application and removal), satisfaction with the bandaging, and ease of application of the bandaging, all

17 elements on a 0-4 scale. Total score ranges from 0 to 4 with higher scores indicating a worse outcome.

- Time Frame: Administered at 1, 2, 4 and 6 weeks post-surgery
- 2. Change in PUSH Score Over Time
 - a. The pressure ulcer scale for healing (PUSH) tool is a validated means of measuring wound healing over time, specifically wounds that heal via secondary intent, by taking into account things like wound size and wound exudate, among others. Scores range from 0-17 with higher scores indicating inferior wound healing.
 - Time Frame: Completed at 1, 2, 4 and 6 weeks post-surgery utilizing images submitted by patients
- 3. Change in Pain with Dressing Changes
 - a. The numeric rating scale (NRS) will be used, where patients will be asked to rate pain with dressing changes and general pain on a scale from 0-10 with higher scores indicating worse pain. This information will be collected in the patient survey that is sent post-operatively.
 - Time Frame: Collected at 1, 2, 4 and 6 weeks post-surgery

Secondary Objective

The PWAT will be an important secondary endpoint for evaluation and comparison with the primary endpoints. Other patient-reported outcomes including interference with daily activities/exercise, assistance needed with bandaging changes, bandage change difficulty, and likelihood to use this bandage type in the future will be assessed. Additionally, patient-reported wound healing will be recorded. This will include questions such as "To what degree is the wound healed?" with answers on a 10-point scale ranging from "completely healed, somewhat healed, not healed." Number of days to wound healing/resolution will be asked on all surveys 4 weeks and later. Patients will also be asked whether or not they believe their wound is showing signs of infection.

2 INVESTIGATIONAL PLAN (brief overview)

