3.3 Follow- up procedures (by visits)

Patients will have no scheduled follow-up visits in person. They will instead receive surveys at weeks 1, 2, 4, 6, and after if necessary. However, patients may schedule an in-person visit at any time.

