3.6 Screen failure procedures

If a patient does not meet inclusion criteria at enrollment, normal clinical care will resume with no detriment to the patient.

4 STUDY EVALUATIONS AND MEASUREMENTS (how measurements will be made)

- List variables that will be abstracted from medical charts

Page **12** of **20**

Baseline demographics including age, sex, race, BMI, smoking history, among others will be recorded from the medical chart and verified with the patient on the day of enrollment.

- Describe baseline evaluation

Baseline evaluation will include identifying surgical site, evaluating if surgical site is optimal for study inclusion, assessment of patient's overall general health,

- Describe how measurements will be taken.

Patient's upload a photo of their wound with each online survey they complete, as well answers to questions such as pain with wound dressing changes on a scale 1-10. Wound measurements and wound characterization for the primary and secondary endpoints will then be completed at the conclusion of the study by the PI. Other questions and data will be inputted by patients directly on the survey for future statistical evaluation.

- Describe rating scales, tests, psychological tools, laboratory evaluations, etc.

The previously-described PUSH, Wound QOL, and NRS primary endpoints will all be recorded and extrapolated from the online surveys submitted by patients at scheduled intervals.

STATISTICAL CONSIDERATIONS

Our study is powered to detect an effect on our primary endpoints, pain and quality of life. Although we will use the Wound Quality of Life (QoL) survey for our main analysis, as it is more comprehensive and we think readers will find it more persuasive, we don't have direct data on what to expect. Rather, we do have a strong sense, from clinical experience, of what will happen with pain. Using the 0-10 numerical pain scale, we believe the non-stick dressing will reduce pain ratings by 1.3 points at the two-week checkup and estimate the historical SD at that visit is 1.4 units, implying a .93 SD reduction. We calculate we will need 28 patients per arm to achieve 80% power. We add 2 more to account for two planned covariates (pelvic area vs armpit, and initial wound size). Since we expect approximately 20% dropout, we will plan to recruit approximately 74 patients.

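### Carry-forward makes no exception for a closed wound, so a healed patient's blank dressing-change pain item is filled with the last open-wound score

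*Combined protocol and SAP*

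**What the plan says.** **Missing data (Section 8, Data Collection and Management).** For gaps within a survey the rule is: "If patients fail to enter data at specific time points on their surveys we will use the previous value carried forward to the missing data". For surveys that do not come back: "The data for patients who do not return their surveys will not be included in the study analysis". Neither sentence mentions wounds that have closed.

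**The pain outcome (Section 1.4, Primary Objectives).** Change in pain with dressing changes is the third primary outcome: "patients will be asked to rate pain with dressing changes and general pain on a scale from 0-10". Its time frame is "Collected at 1, 2, 4 and 6 weeks post-surgery". Section 4 describes the same item differently: "pain with wound dressing changes on a scale 1-10".

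**Healing is foreseen.** In Section 1.4, "Number of days to wound healing/resolution will be asked on all surveys 4 weeks and later". The synopsis and Section 2.3 keep patients beyond week 6 only if the wound is still open.

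**The survey schedule has two forms.** Section 3.3: "They will instead receive surveys at weeks 1, 2, 4, 6, and after if necessary". Section 2.1 has questionnaires going out fortnightly after week 2 and ending at closure.

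**PUSH (Section 1.4).** "Completed at 1, 2, 4 and 6 weeks post-surgery utilizing images submitted by patients", on a scale of 0 to 17 where higher is worse.

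No section says what value dressing-change pain takes once dressings have stopped. A zero, a not-applicable code and truncation at healing are all unmentioned.

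**The concern.** Carry-forward assumes that the previous value is a fair stand-in for the missing one. After closure it is not. The patient has no dressing left to change, and the previous value describes an open wound. A blank that arises because the patient has healed is then recorded as continuing pain, on a primary outcome, in a patient who is still being followed and has returned the survey.

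This is not a dropout problem, so better retention would not remove it. It inflates the late pain means, and it can move the between-arm difference because arms may differ in how many patients heal and in how painful the last open-wound dressing changes were.

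**Working it through.** **1. The plan's own figures.** The sizing section assumes a 1.3-point reduction at week 2 with SD 1.4, and 1.3 / 1.4 = 0.93 SD as stated. The 28 per arm is reproduced by a t-test at two-sided alpha 0.0125 (power 80.9%), although the plan states no alpha for pain. Adding 2 per arm gives 60, and 60 / 0.80 = 75 against the stated 74. Nothing below changes these figures.

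**2. The rule applied to one record (hypothetical).** A patient rates 5 at week 1 and 3 at week 2, heals in week 3, and returns the week-4 survey with the item blank.
- Under Section 8 the record becomes 5, 3, 3. If a week-6 survey is also sent and the item is again blank, it becomes 5, 3, 3, 3.
- A patient with the same course who enters 0 is recorded as 5, 3, 0 (and 0 at week 6).

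**3. Which surveys are exposed.** A patient who heals between two surveys still receives the next one, because that is where closure is first reported. So at least one survey is exposed under either schedule. Later surveys are exposed if Section 3.3 governs. If Section 2.1 governs, they are not sent, and the text does not say whether those time points are carried forward, treated as unreturned or left empty.

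**4. Formula.** Taking dressing-change pain after closure as 0:

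inflation of an arm mean = (share of the arm healed with the item blank) × (mean last open-wound score)

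The shift in the contrast is the difference between the two arms' inflations.

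**5. Illustrations.** The documents give no healing rates, blank-item rates or late pain levels, so every input here is an assumption.
- *Unequal healing, equal last scores.* 0.40 × 2 = 0.80 and 0.25 × 2 = 0.50, a shift of 0.30 against the faster-healing arm. Last scores of 1 and 3 give 0.15 and 0.45. If only half of the healed patients leave the item blank, the shift at a score of 2 is 0.15.
- *Equal healing, unequal last scores.* With 40% in both arms and last scores of 3.0 and 1.7, 0.40 × 3.0 = 1.20 and 0.40 × 1.7 = 0.68. The shift is 0.40 × 1.3 = 0.52 in favour of the arm with the lower last score.
- *Both unequal.* 0.40 × 1.7 = 0.68 in the faster-healing arm and 0.25 × 3.0 = 0.75 in the slower. Here the slower-healing arm is inflated more, by 0.07.

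**6. A wider grid.** Shares healed and blank were 10%, 25% or 50% when equal, and 25% against 10% or 50% against 25% in either direction. Last scores (petrolatum, wet-to-dry) were (2, 2), (2, 3.3) or (4, 5.3).
- Arm means rise by 0.2 (0.10 × 2) to 2.65 (0.50 × 5.3).
- With equal shares, wet-to-dry minus petrolatum shifts by 0 to +0.65 (0.50 × 1.3).
- With unequal shares, it shifts by −0.68 (0.25 × 5.3 − 0.50 × 4 = −0.675) to +1.65 (0.50 × 5.3 − 0.25 × 4).

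The sign changes within plausible-looking inputs.

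**The case against.** **The trigger is assumed.** The survey form is not in the document. A healed patient might enter 0, branching might hide the item, or the recall period might cover dressing changes made before closure. One can also argue that an item that no longer applies is not one the patient failed to complete. Section 8 itself expects few missing points. All of this stands as a limit on size: the point concerns items left blank, and their number is unknown. It does not supply the missing rule.

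**Section 2.1 stops surveys at closure.** This also stands in part. It confines certain exposure to the first survey after closure, and anything later depends on which schedule governs.

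**A reader might infer a known direction:** that the rule penalises the faster-healing arm, or that equal healing leaves the contrast unbiased. Both need equal last open-wound scores in the two arms. The plan hypothesises lower pain on petrolatum, and the second and third illustrations show each inference failing. For the same reason the rule cannot be defended as conservative.

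**A reader might set the late bias against the 1.3-point target.** That target belongs to week 2, when probably few wounds have closed, so a percentage of it would mislead.

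**A reader might extend the point to PUSH and a false non-inferiority finding.** The documents do not support that. A closed wound can still be photographed and scored 0 by the blinded investigator, and Section 4 has a photo uploaded with every survey. A missing photo is ordinary missing data, and nothing shows that healed patients omit it more often. What remains is narrower: if carry-forward is applied to a missing photo after closure, which is a reasonable but not explicit reading, an open-wound score replaces the best possible one.

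**Conclusion.** The concern holds for dressing-change pain. Read literally, the carry-forward sentence gives a wrong value to a blank item on a survey returned after closure, and no other section corrects it. The effect falls on weeks 4 and 6, which belong to the primary outcome's time frame. The week-2 comparison used for sizing is probably little affected, and the sample size is unchanged.

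The size cannot be fixed from the documents. The illustrative shifts of 0.30 and 0.52 points rest on assumed healing shares, assumed last scores, every healed patient counted leaving the item blank, and true post-closure pain of 0. The direction of bias in the contrast is unknown. For PUSH, only a clarification is warranted.

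**What to change.** **Section 8.** Add a sentence to this effect: *carry-forward is not applied to dressing-change NRS at or after the visit at which closure is recorded; a blank at those visits is analysed as 0 (no dressing-change pain), and the number so scored is reported by arm.* Closure can be identified from the healing and days-to-healing items already collected.

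**Sensitivity analysis.** Repeat the dressing-change pain comparison in patients still using a dressing. Scoring closed wounds as 0 is one choice of estimand and treating the item as not applicable is another; this analysis shows the second.

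**PUSH.** Do not carry an open-wound score past closure. Keep scoring from the photo by the blinded investigator. Where closure is reported but no photo exists, show results with 0 and with the value left missing. Imposing 0 as the only analysis would bring an unblinded patient's report into a blinded assessment.

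**Reconcile.** Sections 2.1 and 3.3 on whether surveys continue after closure, including how time points with no survey sent stand under the unreturned-survey rule. Also Sections 1.4 and 4 on whether the pain item runs 0–10 or 1–10, since a 1–10 item offers a healed patient no zero.

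**Cost.** A few sentences and one or two short tables, with no extra patients or visits. The document is dated 8/1/2024, gives study dates ending in October 2023 and records actual enrollment of 74. A new survey response option is therefore probably too late, but the analysis rule can still be written. The drawback is that late dressing-change pain will partly reflect healing, which the sensitivity analysis makes visible.
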